3.3. Description of Study Hypotheses

This study is designed as a proof-of-concept study. It is therefore not formally powered for the primary endpoint. The purpose of the trial is to determine if there is an adequate treatment effect to proceed to a pivotal study. It is planned to randomize approximately 90 subjects (45 per group) to achieve 80 evaluable subjects (for the primary efficacy endpoint analysis).

Primary Efficacy Endpoint

The primary efficacy endpoint of the change in mean 24-hour ambulatory SBP at 8 weeks post-treatment will be compared between the 2 treatment groups.

The following table provides examples of observed treatment effects and standard deviations (SDs) that would be considered statistically significant at alpha = 0.05, for the change in mean 24-hour ambulatory SBP at 8 weeks post-treatment with 80 evaluable subjects:

Treatment Difference	Standard Deviation
3.5 mmHg	8 mmHg
4.4 mmHg	10 mmHg
5.3 mmHg	12 mmHg

A study of the planned size would be powered at 80% to detect a difference between intervention and control of 5.1 mmHg assuming a SD of 8 mmHg in each group and two-sided alpha of 0.05 using the independent two-sample t-test. A difference between treatment and control of 5 mmHg is considered clinically meaningful and consistent with previous trials of renal denervation in a similar population (Townsend et al. 2017). An observed difference between groups of 5 mmHg with an observed SD as high as 11.2 mmHg per group would be considered statistically significant at a two-sided alpha level of 0.05.

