5.2.2. Adjustments for Covariates

Analysis of changes in blood pressure measures will be adjusted for baseline values using analysis of covariance (ANCOVA). Raw mean values will be presented, however, comparisons between groups will include the baseline value of the associated measure as described below. There is no other planned adjustment for covariates.

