An additional exploratory analysis will be conducted, which combines the treatment failures (subjects receiving rescue medication) with the continuous 24-hour ambulatory SBP measurement in a hierarchical fashion using the approach described in Finkelstein and Schoenfeld (1999) and later adapted to the Win Ratio by Pocock (2012). Using this approach, each subject is compared to every other subject first as to whether or not the subject received rescue medication. If both subjects did or did not receive rescue medication (i.e., there is a tie), then the subjects will have their change in 24-hour ambulatory SBP at 8 weeks compared. A score of -1 will be assigned to a loss and a score of +1 will be assigned to a win. For example:

- If Subject A receives rescue medication within 8 weeks and Subject B does not, Subject A loses (score -1), and Subject B wins (score +1)
- If neither receive rescue medication within 8 weeks, then if Subject A has a larger reduction in 24-hour ambulatory SBP at 8 weeks compared to Subject B, then Subject A wins (score +1) and Subject B loses (score -1).

After all between-subject comparisons have been performed, scores will be summed to obtain a cumulative score for each subject, and the scores between treatment groups will be compared using the Mann-Whitney U test. The resulting p-value will be presented. The win ratio will also be presented. It is calculated as number of "wins" divided by the number of losses out of all comparisons of intervention to sham subjects.

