7. CHANGES TO THE STATISTICAL ANALYSIS PLAN

Version / Date	Old Analysis	New Analysis	Reason for change
2.0 28Sep2020	n/a	Telephone contacts at 2 and 6 weeks in Ireland only added.	Updated per Protocol V6.0
		Those protocol deviations associated with COVID-19 will be additionally summarized separately.	Per FDA guidance
		Subgroups added:Region (US vs Europe)Ethnicity (US only)Race (US only)	Updated per Protocol V6.0
		Analysis windows clarified and description expanded	Clarification
		Added repeated measures analysis of blood pressure.	Oversight
3.0 08Dec2020	8-week primary analysis window not defined, assumed to be per the protocol	8-week primary analysis window expanded.	Addition, clarification
	No imputation specified for primary analysis	Imputation of data for subjects who meet the criteria for antihypertensive drug treatment for the primary analysis clarified.	Clarification
	n/a	Sensitivity analyses added for all 8-week BP measures	Addition
	n/a	Exploratory hierarchical analysis added	Addition
	Comparison between groups for BP measurements via t-test	Comparison between group for BP measures by ANCOVA adjusting for baseline BP	Per FDA guidance for the Target BPI study, and for consistency between the 2 studies
4.0 19Nov2021	n/a	Two unblinded team members (either two statisticians or a statistician and a statistical programmer) will be assigned for all analyses.	CAPA-00012

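### The exploratory win-ratio analysis ranks rescue-tied pairs on raw change in 24-hour SBP, while the SAP's other 8-week BP comparisons adjust for baseline: a minor inconsistency and an avoidable loss of precision

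*SAP*

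**What the plan says.** SAP 5.4.1 adds an exploratory analysis that combines rescue medication with 24-hour SBP. Each pair of subjects is compared first on rescue. If that is a tie, "then the subjects will have their change in 24-hour ambulatory SBP at 8 weeks compared", and the larger reduction wins. Scores are summed per subject and "the scores between treatment groups will be compared using the Mann-Whitney U test"; a p-value and the win ratio are reported. No baseline adjustment is mentioned.

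SAP 5.2.2 says that changes in BP are analysed by ANCOVA on baseline and that "comparisons between groups will include the baseline value of the associated measure as described below". SAP 5.4.1 applies this to the primary analysis of the same variable. The change log in SAP 7 shows that version 3.0 brought in both the ANCOVA ("Comparison between group for BP measures by ANCOVA adjusting for baseline BP", replacing a t-test) and the hierarchical analysis, as separate entries.

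The planning statement in SAP 3.3 describes a study "powered at 80% to detect a difference between intervention and control of 5.1 mmHg", "assuming a SD of 8 mmHg in each group", with "two-sided alpha of 0.05 using the independent two-sample t-test". The plan is to "randomize approximately 90 subjects (45 per group) to achieve 80 evaluable subjects". SAP 5.2.1 and 5.2.6 say that there is no formal hypothesis testing.

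**The concern.** The primary ANCOVA and the hierarchical analysis will be read side by side to see what counting rescue changes. They differ in a second respect: one adjusts for baseline and the other does not. On raw change, a subject with a high baseline tends to win through regression to the mean, so chance baseline imbalance moves the win ratio and its p-value. A difference between the two results could then be credited to the rescue component when it comes only from baseline. The covariate is already collected: inclusion criterion 9 in the Protocol synopsis requires a valid 24-hour ABPM at the end of run-in.

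**Working it through.** **Inputs from SAP 3.3:** 80 evaluable subjects, taken as n = 40 per arm; difference 5.1 mmHg; SD of change 8 mmHg; two-sided alpha 0.05.

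**Assumed, because the documents give no figure:** the baseline/8-week correlation rho, the ratio k of baseline SD to 8-week SD, and rescue rates.

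**Step 1: the plan's own figure.** SE = 8 × √(2/40) = 1.789. Power ≈ Φ(5.1/1.789 − 1.96) = Φ(0.891) = 81.4%. The noncentral t gives 80.4%. The stated 80% is reproduced.

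**Step 2: what adjustment does to the SD.** If the 8-week SD is s and the baseline SD is ks, then
- variance of change = s²(1 + k² − 2·rho·k)
- variance of 8-week SBP given baseline = s²(1 − rho²)
- proportion of variance removed = (k − rho)² / (1 + k² − 2·rho·k)

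With k = 1 the adjusted SD is 8 × √((1 + rho)/2), which is 6.93 at rho 0.5. The gain vanishes when k equals rho. Holding the SD of change at 8:
- k = 0.8, rho 0.5: removed 0.09/0.84 = 10.7%, SD 7.56
- k = 0.7, rho 0.5: removed 0.04/0.79 = 5.1%, SD 7.79
- k = 0.8, rho 0.7: removed 0.01/0.52 = 1.9%, SD 7.92
- k = 0.8, rho 0.8: removed 0, SD 8.00

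**Step 3: power of the hierarchical test.** Simulation of the rank test on the hierarchical order, 40 per arm, 40,000 trials per row, no rescue, k = 1:

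| rho | raw change | baseline-adjusted | gain (points) |
|---|---|---|---|
| 0.3 | 77.9% | 92.4% | 14.5 |
| 0.4 | 78.4% | 90.6% | 12.2 |
| 0.5 | 78.1% | 88.7% | 10.7 |
| 0.6 | 78.3% | 86.7% | 8.4 |
| 0.7 | 78.2% | 84.4% | 6.2 |
| 0.8 | 78.2% | 82.4% | 4.2 |

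This table takes the slope within arms. A fit pooled over arms, simulated separately with 6,000 trials, gave 88.2% at rho 0.5. By noncentral t the gain at rho 0.5 is 9.8 points (80.4% to 90.2%).

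**Step 4: unequal SDs at rho 0.5.** The gain is 7.6 points at k = 0.9, 4.8 at 0.8, 2.4 at 0.7 and 0.7 at 0.6. At k = 0.8 and rho 0.7 to 0.8 it is about zero, as Step 2 implies.

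**Step 5: rescue at rho 0.5, k = 1.** At assumed rates (treatment/sham) of 5%/5% the gain is 11.7 points, at 5%/10% it is 9.3, and at 10%/20% it is 7.6. With 5% in each arm, 0.95² + 0.05² = 90.5% of between-arm pairs are tied on rescue and go to the BP tier.

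**Step 6: validity.** With no treatment effect at rho 0.5, k = 1, rejection is 4.8% on raw change and 5.3% on adjusted change.

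**Step 7: comparability.** At rho 0.5, k = 1 and no rescue at all, the raw hierarchical test and the ANCOVA fell on different sides of 0.05 in 14% of simulated trials; with the residual tier it was under 4%. As a hand check on imbalance, the baseline SD in this case is 8 mmHg, so one standard error of the baseline difference is 1.79 mmHg. The slope of change on baseline is rho − 1 = −0.5, which shifts mean change by 0.89 mmHg. With no treatment effect, P(win) = Φ(0.89/(8√2)) = 0.531 and the win ratio is 0.531/0.469 = 1.13. Two standard errors give 1.29.

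**The case against.** **No rule is clearly broken.** A reader might infer that the hierarchical analysis violates SAP 5.2.2. The documents do not go that far. That section ties adjustment to ANCOVA and to comparisons described later in the SAP, and the log records the ANCOVA as replacing a t-test, separately from the hierarchical addition. A rank-based composite can be read as outside the rule. This stands: it is an inconsistency to clarify, not a contradiction.

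**Power is a weak yardstick.** The analysis is exploratory, no power is stated for it, and the only planning figure is for an unadjusted t-test. The 78% on raw change is close to that figure, so nothing promised is lost. This also stands.

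**A loss of about 11 points is not a property of the plan.** It needs rho 0.5 and equal SDs, neither of which is in the documents. Entry confines baseline 24-hour SBP to 135-170 mmHg, with no such limit at 8 weeks, so k below 1 is plausible and the gain may be under 5 points or nil.

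**Rescue is also handled elsewhere.** Sensitivity analyses 1, 2, 3 and 5 in SAP 5.4.1 vary the primary analysis for rescue. But none of them ranks rescue and BP together, and calling the analysis exploratory does not explain why it uses a different metric from the ANCOVA beside it.

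**Conclusion.** The point holds as a minor, optional improvement. The second tier uses raw change where the adjacent primary analysis adjusts for baseline, and the SAP does not say that this is intended. The cost is precision and comparability with the ANCOVA.

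The gain from adjustment, with the plan's inputs and no rescue, is about 4 to 15 points of power for rho 0.8 to 0.3 with equal SDs. At rho 0.5 it is about 10 points with equal SDs, 4 to 5 at k = 0.8 and about 2 at k = 0.7. It is about zero at rho 0.7 to 0.8 with k = 0.8. All of these rest on assumed rho and k.

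A reader might also infer that the win-ratio p-value is invalid or biased. It is not: chance baseline imbalance is part of the sampling variation that the test allows for, and type I error stays at about 5%. No decision is tied to this result.

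**What to change.** In SAP 5.4.1, compare pairs tied on rescue by baseline-adjusted 8-week 24-hour SBP: the residual from a regression of 8-week SBP on baseline 24-hour SBP, pooled over arms and fitted in subjects without rescue medication. For any rescued subject with an 8-week value, compute the residual from the same fit. The lower residual wins. The last two conditions are needed because SAP 5.4.1 otherwise accepts 8-week ABPM only off medication, which leaves the place of rescued subjects in the regression open. Keep the raw-change version as a supplementary row in Table 14.2.2-4.

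If the sponsor prefers raw change because it is more direct, one sentence saying that the analysis is deliberately unadjusted would remove the inconsistency, though not the loss of precision.

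The cost is about a sentence in the SAP and a few lines of code. The downside is that a residual is a little harder to explain than a reduction in mmHg; the supplementary row covers that.

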5.5. Secondary Endpoints

In general, all secondary efficacy endpoints will be summarized in the ITT Analysis Set and the PP Analysis Set (if it differs from ITT). All secondary safety endpoints, with the exception of

Device and Procedure Success, will be summarized in the Safety Analysis Set. Device and Procedure Success will be summarized in the ITT Analysis Set.

5.5.1. Secondary Safety Endpoints

5.5.1.1. MAE within 30 days

The number and percent of subjects experiencing any MAE within 30 days as adjudicated by the clinical events committee will be summarized and two-sided 95% exact CIs will be reported. The difference between groups will be summarized, two-sided 95% exact Cis will be reported and the groups will be compared via the Fisher's Exact test. Only subjects who have experienced an MAE within 30 days or who have at least 21 days of follow-up (includes subjects who have had their 4 weeks visit minus the allowable visit window). These analyses will be conducted in the Safety Analysis Set.

5.5.1.2. Changes in eGFR from Baseline to 8 weeks and 6 months Post-Treatment

The change in eGFR will be summarized between baseline and 8 weeks and baseline and 6 months. Changes in eGFR at 8 weeks and 6 months will be compared between groups using the independent two-sample t-test. These analyses will be conducted in the Safety Analysis Set.

5.5.1.3. Decreases in eGFR >25% from Baseline to 8 weeks and 6 months Post-Treatment
The number and percent of patients with greater than a 25% reduction in eGFR will be summarized at 8 weeks and 6 months. Groups will be compared using Fisher's Exact test. These analyses will be conducted in the Safety Analysis Set.

5.5.1.4. Rate of Adverse Events (Serious and Non-Serious), Peri-Procedurally, at Discharge, and at Each of the Follow-up Time Points.

Coded AEs will be summarized at each follow-up time period (any events occurring prior to and including the follow-up time) and overall according to system organ class (SOC) and Preferred Term (PT) by treatment group as described in Section 5.8.1 below.

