- Significant acute (post-procedural) renal artery stenosis (>60% diameter stenosis) as indicated by the renal angiogram post renal denervation, and confirmed by the angiography core laboratory, which led to one of the following: (i) acute kidney injury per modified Risk, Injury, Failure, Loss of kidney function, and End-stage kidney disease (RIFLE) definition, as confirmed by renal function blood test, or (ii) percutaneous intervention.
- Hypertensive crisis (hypertensive emergency only)
- Hypotensive crisis
- Symptomatic hypotension that required a change in antihypertensive medications, or medications to increase blood pressure (e.g. persistent syncope, lightheadedness)
- Changes in eGFR from baseline to 8 weeks, 6 months, and 1-year post-treatment.
- Decreases in eGFR >25% from baseline to 8 weeks, 6 months, and 1-year post-treatment.
- Rate of adverse events (serious and non-serious), peri-procedurally, at discharge, and at each of the follow-up time points.
- Device success (defined as the ability to insert the Peregrine Catheter into the lumen of the renal artery [target vessel], deploy the guide tubes inside the renal artery, deploy the needles through the arterial wall, deliver the intended dose of alcohol, retract the needles and the guide tubes back in the catheter, and remove the catheter from the access site without any related complications or events)
- Procedure success (defined as device success with freedom from peri-procedural MAEs).

The percentage of subjects with any MAE through 30 days post-treatment will be displayed by treatment group. The relative risk will be displayed with 95% CIs. The 2 groups will be compared using Fisher's exact test.

Other safety endpoints will be summarized as frequencies and percentages. Relative risks and 95% CIs will be computed. Analysis of all safety endpoints will be conducted using the Safety Analysis Set.

Table 1 Schedule of Study Assessments (Main Study)

Period	Scrn Period	Run-In Period ¹			In-Hospital Period		Follow-Up Period					ET ²	
Visit Time Point	Up to Wk -8	Wk -4	Wk -2	Wk -1 (Baseline)	D 0 ³	D 1	D 2 to D 4 (48-96 h) ⁴	Wk 4	Wk 8	Mth 3	Mth 6	Yr 1 and 2	
Visit Window			+/-4 D	+/-2 D				+/-7 D	+/-7 D	+/-2 Wk	+/-4 Wk	+/-8 Wk	
Informed consent	X												
Eligibility check	X			X									
Demographic data	X												
Medical history	X												
Office BP pressure ⁵	X		X	X				X	X	X	X	X	X
24-hour ABPM ⁶				X ⁷					X		X		X ⁸
MRA/CTA ⁹	X ¹⁰											X ¹¹	

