- 3 Subjects with an eGFR of >45 and <60 mL/min/1.73 m² based on the Week -1 (baseline) serum creatinine sample will undergo blood sampling for post-contrast serum creatinine measurement 48-96 hours after imaging during the procedure and any subsequent procedure where imaging contrast is used.
- 4 eGFR will be calculated using the Chronic Kidney Disease Epidemiology Collaboration (CKD-EPI) equation. For all subjects, if the calculated eGFR is reduced >25% from baseline (Week -1), the investigator should repeat the serum creatinine test as soon as possible, but no later than 1 week after the first test. If the repeated calculated eGFR remains >25% from baseline, the investigator should refer the subject for further renal functions evaluations, including review by a nephrologist. Similarly, if a subject's eGFR drops to ≤45 mL/min/1.73 m², then he/she will have renal function monitored and managed by a nephrologist as an additional safety measure following this event and until the event is resolved. In either case, the decrease in eGFR will be reported as an AE.
- 5 Only calculated for those subjects who have serum creatinine measured at this time point.
- 6 Performed per the hospital's standard of care and analyzed at site.
- 7 Compliance testing in relation to antihypertensive medications.

Table 4 Schedule of Blood and Urine Sample Collection (Crossover Phase)

[figure not shown]
Period		Re-Screening Period	Treatment	Follow-Up Period		
Visit Time Point		Up to Wk -4	D 0	D 2 to D 4 (48-96 h) ¹	Wk 4	Mth 6
Visit Window					+/-7 D	+/-4 Wk
Serum chemistry	Sodium	X			X	X
	Potassium	X			X	X
	Serum chloride	X			X	X
	BUN/urea	X			X	X
	Uric acid	X			X	X
	Cystatin C	X			X	X
	Glucose	X			X	X
	Serum creatinine	X		X ²	X	X
	eGFR ³	X		X ⁴	X	X
Liver panel	AST (SGOT)	X			X	X
	ALT (SGPT)	X			X	X
	Alk phos	X			X	X
	Bilirubin (conj)	X			X	X
	Bilirubin (total)	X			X	X
	LDH	X			X	X
	Albumin	X			X	X
	Total protein	X			X	X
Hematology	RBC	X			X	X
	WBC (total and differential)	X			X	X
	HGB	X			X	X
	HCT	X			X	X
	Platelets	X			X	X

Period		Re-Screening Period	Treatment	Follow-Up Period		
Visit Time Point		Up to Wk -4	D 0	D 2 to D 4 (48-96 h) ¹	Wk 4	Mth 6
Visit Window					+/-7 D	+/-4 Wk
Coagulation	aPTT	X				
	PT	X				
	INR	X				
	ACT ⁵		X			
Urinalysis	Specific gravity	X			X	X
	pH	X			X	X
	Glucose	X			X	X
	Ketones	X			X	X
	Protein (total)	X			X	X
	Bilirubin	X			X	X
	Hemoglobin	X			X	X
	Nitrite	X			X	X
	WBC	X			X	X
	RBC	X			X	X
	Bacteria	X			X	X
	Crystals	X			X	X
	Casts	X			X	X

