4. PATIENT POPULATIONS

4.1. Data Sets to be Analyzed

The Intent-to-Treat (ITT) Analysis Set will include all subjects who were randomized regardless of whether treatment was received. Subjects will be analyzed according to their randomized treatment group, irrespective of treatment received.

The Safety Analysis Set will include all subjects who received treatment. Subjects will be analyzed according to the actual treatment received, irrespective of treatment assignment.

The Per-Protocol (PP) Analysis Set will include subjects with no important protocol deviations. Subjects will be analyzed according to the actual treatment received. Important protocol deviations include:

- Not meeting inclusion/exclusion criteria
- Not receiving bi-lateral treatment or an unsuccessful procedure
- Receiving anti-hypertensive treatment prior to evaluation of the primary ambulatory blood pressure monitoring (ABPM) measurement
- Not completing the primary ABPM measurement

All deviations will be reviewed prior to unblinding to assess if additional exclusions will be applied.

Unless otherwise noted, the ITT and PP Analysis Sets will be used for all efficacy analyses and safety analyses will be conducted in the Safety Analysis Set.

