5.2. General Considerations

5.2.1. General Methods

Two unblinded team members (either two statisticians or a statistician and a statistical programmer) will be assigned for all analyses. This will allow for discussion of output and direct QC of statistical programming on the exact same dataset.

In general, continuous variables will be summarized with descriptive statistics (n, mean, SD, range, median, and interquartile range). The difference between groups will be presented and the normal approximation will be used to calculate two-sided 95% confidence intervals (CIs). Change from baseline, when relevant, will be computed as the paired mean difference and 95% CI of the mean difference at each time point.

For all continuous primary and secondary blood pressure endpoints, changes over time will be additionally explored in mixed effects repeated measures analyses, including the values at all time points.

Categorical variables will be summarized as frequencies and percentages. Relative risks and 95% CIs will be computed.

All statistical analyses will be performed using SAS® Version 9.4 or higher (SAS Institute, Cary, NC 27513, USA).

For each variable, the baseline value will be defined as the last value collected before the procedure.

There will be no formal hypothesis testing conducted in the study. Ninety-five percent CIs, when presented, are intended to be descriptive in nature only. For binary variables, CIs will be calculated via exact binomial methods. For continuous variables, the CI of the mean will be constructed using the normal approximation.

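### eGFR change is compared by an unadjusted t-test although Week -1 eGFR is available; baseline-adjusted ANCOVA would give a modest gain in precision and robustness to chance imbalance

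*SAP*

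**What the plan says.** SAP 5.5.1.2 summarizes the change in eGFR and names the comparison: "Changes in eGFR at 8 weeks and 6 months will be compared between groups using the independent two-sample t-test". The analysis uses the Safety Analysis Set, for which SAP 4.1 says: "Subjects will be analyzed according to the actual treatment received, irrespective of treatment assignment".

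SAP 5.2.2 compares blood pressure changes by ANCOVA on the baseline value, with raw means also shown, and then closes the list: "There is no other planned adjustment for covariates". No other SAP section adjusts eGFR for baseline.

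The covariate exists. Protocol Table 3 schedules serum creatinine and eGFR at Week -1, and its eGFR footnote treats that value as the reference for everyone: "For all subjects, if the calculated eGFR is reduced >25% from baseline (Week -1), the investigator should repeat the serum creatinine test". SAP 5.2.1 supplies the analysis definition: "For each variable, the baseline value will be defined as the last value collected before the procedure".

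The change log in SAP section 7 shows that version 3.0 moved the blood pressure comparisons from t-test to ANCOVA, with this reason: "Per FDA guidance for the Target BPI study, and for consistency between the 2 studies". eGFR is not mentioned there.

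The protocol synopsis lists the endpoint as "Changes in eGFR from baseline to 8 weeks, 6 months, and 1-year post-treatment" and names no test for it.

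**The concern.** Kidney function is a central safety question for a procedure that delivers alcohol through the renal artery wall, and mean eGFR change by arm is one of the figures readers will look at. A t-test on change subtracts the baseline in full. That is more correction than regression to the mean warrants, so an arm that starts higher by chance tends to show the larger fall.

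Nothing in the design balances baseline eGFR. Randomization is stratified by site only, with about 90 subjects over about 25 sites. Eligibility sets a lower limit on eGFR and no upper one. SAP 5.2.7 itself expects a spread, with groups of 45-60, 61-75 and above 75.

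At stake are a somewhat wider interval than the data allow and an estimate that carries part of any baseline difference. Pre-specifying the adjustment would also avoid a post hoc choice if baseline eGFR proves uneven.

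**Working it through.** **The plan's own figure.** The documents give no SD, correlation or power for eGFR. The nearest stated figure is for the primary endpoint (protocol sample size section, SAP 3.3): 80% power for 5.1 mmHg, SD 8 mmHg, two-sided alpha 0.05, 80 evaluable subjects. With 40 per arm the power is 80.4% by the noncentral t, so the figure reproduces. I use the same 40 per arm (N = 80) for eGFR.

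**Assumptions.** eGFR has the same SD (s) at baseline and follow-up. The baseline/follow-up correlation rho is varied from 0.5 to 0.98, because the documents do not state it.

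**Precision.** Variance of the between-arm difference:

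- t-test on change: 2 s²(1 - rho) × (2/40)
- ANCOVA: s²(1 - rho²) × (1 + 1/(N - 4)) × (2/40). The factor 1 + 1/76 is the small-sample cost of estimating the slope.
- Ratio, ANCOVA to t-test: [(1 + rho)/2] × (77/76)

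At rho 0.7 this is 0.85 × 1.0132 = 0.861. Its square root is 0.928, so the standard error is 7.2% lower.

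| rho | Variance ratio | SE lower by | Subjects ANCOVA needs to match the t-test at 80 |
|---|---|---|---|
| 0.5 | 0.76 | 13% | 61 |
| 0.7 | 0.86 | 7% | 69 |
| 0.8 | 0.91 | 4.5% | 73 |
| 0.9 | 0.96 | 2% | 77 |
| 0.95 | 0.99 | 0.6% | 79 |

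The ratio reaches 1 when (1 + rho)/2 = 76/77, that is rho = 75/77 = 0.974. Above that ANCOVA gains nothing; at 0.98 the ratio is 1.003.

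**Chance imbalance.** Let D be the observed baseline difference between arms. With no treatment effect, the expected follow-up difference given D is rho × D, so the expected difference in change is rho × D - D = -(1 - rho)D. For D = 5 mL/min/1.73 m² the size of the shift is:

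- rho 0.7: 0.3 × 5 = 1.5
- rho 0.8: 0.2 × 5 = 1.0
- rho 0.9: 0.1 × 5 = 0.5

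How large is a D of 5? With an assumed baseline SD of 15, the SE of D is 15 × sqrt(2/40) = 3.35, so 5 is about 1.5 SE. Chance gives a difference at least that large, in either direction, in roughly 1 trial in 7.

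**Simulation** (20,000 trials per rho, 40 per arm, no treatment effect). Over all trials the t-test rejects in 4.8% to 5.1%. Among trials with a baseline imbalance above 1.5 SE it rejects in about 12% (rho 0.5), 10% (0.7), 8% (0.8) and 6% (0.9 and 0.95). When the imbalance exceeds 1.5 SE in one direction (about 6.5 units on average), the mean t-test estimate is -1.8 at rho 0.7 and -0.7 at rho 0.9. The mean ANCOVA estimate stays within about 0.1 of zero at every rho.

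**The case against.** The strongest reply is that nothing here is wrong. A t-test on change is a valid comparison. SAP 5.2.2 and 5.5.1.2 agree with each other, and the reason logged for the move to ANCOVA concerns blood pressure only. SAP 5.2.1 says that there is no formal hypothesis testing and that intervals are descriptive. Renal safety does not rest on this one comparison: falls of more than 25% are compared by Fisher's exact test (5.5.1.3), eGFR change is explored within baseline-eGFR groups (5.2.7), laboratory shift tables are planned (5.10), and the protocol requires repeat testing, referral and AE reporting after a large fall. The size of the gain depends on a correlation that the documents do not give.

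Much of this stands. Three stronger readings are tempting, and the documents support none of them:

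- *The t-test is biased or inflates type I error.* It does neither over all randomizations; the shift appears only conditional on an observed imbalance. As-treated analysis could weaken the protection of randomization, but the documents give no expected number of misallocated treatments.
- *Version 3.0 overlooked eGFR, so the SAP contradicts itself.* The closing sentence of 5.2.2 makes the limit to blood pressure look deliberate.
- *A renal safety conclusion could be overturned.* A shift of 0.5 to 1.5 is small beside the plan's flag for an individual: a 25% fall from 60 is 15 units. A mean difference and an individual threshold are different scales, but no decision rule in the plan turns on this comparison.

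Two parts do not dispose of the point. Descriptive status does not make a less precise estimate preferable, and 5.5.1.2 still names a between-group test. The subgroups, responder comparison and shift tables give no baseline-adjusted overall estimate.

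**Conclusion.** The point holds as an optional improvement of low severity. Adjusting for Week -1 eGFR would narrow the interval by an amount that matters at rho 0.5 to 0.7 (13% to 7%), is small at 0.9 (2%) and is negligible from 0.95 upward. It would also remove a dependence on chance baseline imbalance worth 0.5 to 1.5 mL/min/1.73 m² for each 5 units of imbalance at rho 0.9 to 0.7.

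The wording of the plan is certain; the size is not. It rests on equal SDs, 40 evaluable subjects per arm and an assumed rho. Placing 5 units at about 1.5 SE also rests on an assumed baseline SD of 15.

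**What to change.** In SAP 5.5.1.2, report the between-group difference in eGFR with its 95% CI from ANCOVA on baseline (Week -1) eGFR at each analyzed eGFR visit. Show raw mean changes alongside, as is done for blood pressure, and extend 5.2.2 to cover eGFR.

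Timing decides how to introduce it. SAP 5.2.4 allows aggregate results by treatment group to leave the DSMB at the 8-week interim. SAP version 4.0 is dated 19 November 2021, after the protocol's planned primary endpoint completion of June 2021. The documents do not say whether by-arm data have been released. If they have, keep the planned t-test and add ANCOVA as a supportive analysis, so that the change cannot look data-driven.

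The cost is small edits to two SAP sections and to the shell and programming of Table 14.3.7-1. No new data, visits or subjects are needed.
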